7.2.2 Rationale for the Dose Selection and Dose Regimen

A single dose administration regimen has been chosen for this study. Pharmacokinetic data from multiple dose administration at doses between 7.5 and 50 mg twice daily (BID) of MK-7264 demonstrate accumulation of 1.4 to 1.5-fold. This accumulation was well predicted by the single-dose data, with no observed time-dependent non-linearities. Thus the characterization of the single dose pharmacokinetics of MK-7264 in subjects with renal impairment should be sufficient to define appropriate adjustments in dosing with chronic administration of MK-7264 in this patient population.

Single and multiple doses of MK-7264 up to 1800 mg BID have been generally well tolerated in healthy subjects, with the most common dose-related AEs associated with taste disturbance (dysgeusia, ageusia, hypogeusia). In the rising single dose study MK-7264-001, taste disturbance related AEs were observed at doses of 200 mg or greater, and not at doses of 100 mg or lower. In the multiple dose studies, the incidence of taste related AEs at 50 mg BID of MK-7264 ranged from 58% to 81% of subjects. A recently completed Phase 2b study in patients with chronic cough indicated that a 50 mg BID dose of MK-7264 was the dose where maximum efficacy in reducing the frequency of awake cough was reached.

Therefore, the dose proposed in this study will be 50 mg, which will be the highest potential dose in the Phase 3 program, in order to provide information regarding the effect of RI on the pharmacokinetics of a therapeutic dose of MK-7264.

Given the margin between the single dose of 50 mg and the 1800 mg dose that has been generally well tolerated, subjects with severe and moderate renal impairment may be administered a single oral 50 mg dose of MK-7264 in parallel in this study.

7.2.3 Rationale for Endpoints

The primary objective of this study is to evaluate the pharmacokinetic profile of MK-7264 in subjects with impaired renal function. This study will compare the overall pharmacokinetic profile of MK-7264 in subjects with impaired renal function to that of healthy subjects, and this will be assessed by overall exposure (AUC $0-\infty$), C_{max}, CL/F and CL_r.

For ESRD subjects only, CLD,plasma, CLD,dialysate, AD, and AD,total will provide a measure of the extent of MK-7264 removal by HD.

7.2.4 Rationale for Planned Exploratory Biomarker Research

Planned Genetic Analysis

Understanding genetic determinants of drug response and the molecular basis of disease is an important endeavor during medical research. This research will evaluate whether genetic variation within a clinical trial population correlates with response to the treatment(s) under evaluation and/or disease. If genetic variation is found to predict efficacy or adverse events, the data might inform optimal use of therapies in the patient population. Knowledge of the molecular basis of disease contributes to the development of novel biomarkers and the identification of new drug targets. This research contributes to understanding molecular basis of disease and the genetic determinants of efficacy and safety associated with the treatments in this study.

7.2.5 Rationale for Future Biomedical Research

The Sponsor will conduct Future Biomedical Research on DNA specimens consented for future biomedical research during this clinical trial.

Such research is for biomarker testing to address emergent questions not described elsewhere in the protocol (as part of the main trial) and will only be conducted on specimens from appropriately consented subjects. The objective of collecting/retaining specimens for Future Biomedical Research is to explore and identify biomarkers that inform the scientific understanding of diseases and/or their therapeutic treatments. The overarching goal is to use such information to develop safer, more effective drugs/vaccines, and/or to ensure that subjects receive the correct dose of the correct drug/vaccine at the correct time. The details of this Future Biomedical Research sub-trial are presented in [Appendix 2 - Collection and Management of Specimens for Future Biomedical Research](#).

8 STUDY OBJECTIVES, ESTIMATION, AND ENDPOINTS

8.1 Objectives and Estimation

8.1.1 Primary

Both Parts:

Objective: To evaluate the plasma pharmacokinetics of MK-7264 administered to subjects with varying degrees of RI compared to healthy matched control subjects.

Estimation: In subjects with moderate and severe RI, and subjects with ESRD, pharmacokinetic parameters (AUC_{0-∞}, AUC_{0-last}, C_{max}, CL/F, and CL_r, as appropriate) of MK-7264 following administration of a single 50 mg dose will be estimated and compared to those observed in healthy matched control subjects.

Part 2 Only:

Objective: To investigate the extent of MK-7264 removal by hemodialysis.

Estimation: The extent to which MK-7264 is removed from plasma by hemodialysis will be estimated following administration of a single 50 mg dose of MK-7264 in subjects with ESRD requiring hemodialysis.

8.1.2 Secondary (Both Parts)

Objective: To evaluate the safety and tolerability of MK-7264 in subjects with moderate and severe RI (Part 1) and in subjects with ESRD on hemodialysis (Part 2).

8.1.3 Exploratory

Objective 1 (both parts): To estimate and compare the pharmacokinetic parameters (AUC₀₋₁₂, AUC₀₋₂₄, AUC₀₋₄₈, Ae₀₋₂₄, Ae₀₋₄₈, T_{max}, V_{z/F}, apparent terminal t_{1/2}, and Fe, as applicable) between subjects with various degrees of RI and healthy matched control subjects.

Objective 2 (both parts): Analyze the potential relationship between appropriate MK-7264 pharmacokinetic parameters and renal function.

Objective 3 (Part 2 only): To estimate pharmacokinetic parameters (AUC_D, AUC[2.5-6]C_a, AUC[2.5-6]C_v, CLD, plasma, CLD, dialysate, AD, AD, total) for MK-7264 in subjects with ESRD following dosing, as appropriate.

8.1.4 Planned Exploratory Biomarker (Both Parts)

Objective: To explore the relationship between genetic variation and response to the treatment(s) administered, and mechanisms of disease. Variation across the human genome may be analyzed for association with clinical data collected in this study.

8.2 Analysis Endpoints

Pharmacokinetics:

Part 1

The primary pharmacokinetic endpoints will include AUC_{0-∞}, AUC_{0-last}, C_{max}, and CL/F in plasma and CL_r in urine, as appropriate, for MK-7264 in subjects with RI versus healthy matched subjects.

The pharmacokinetic parameters AUC₀₋₁₂, AUC₀₋₂₄, AUC₀₋₄₈, Tmax, apparent terminal t_{1/2}, and V_z/F in plasma, and A_{e0-24}, A_{e0-48}, and F_e in urine, as appropriate, for MK-7264 will also be computed.

Part 2

The primary pharmacokinetic endpoints will include AUC_{0-∞}, AUC_{0-last}, C_{max}, CL/F, AUC_D, AUC(2.5-6)Ca, and AUC(2.5-6)Cv, as appropriate, for MK-7264 in subjects with ESRD in plasma following the HD dosing versus non-HD dosing.

The following pharmacokinetic parameters will also be calculated for MK-7264 in plasma following the HD and non-HD dosing, as appropriate: AUC₀₋₁₂, AUC₀₋₂₄, AUC₀₋₄₈, Tmax, apparent terminal t_{1/2}, V_z/F, CLD_{plasma}, CLD_{dialysate}, AD, and AD_{total}.

Safety:

Safety endpoints will include adverse events, physical examinations, vital signs, 12-lead ECGs, and clinical laboratory tests.

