- m. During HD, blood samples for MK-7264 will be collected from both the pre-dialyzer and post-dialyzer blood lines in addition to peripheral PK blood draw; thus 3 samples per time point during HD will be taken. A blood sample (a pre-dialyzer and post-dialyzer) will also be obtained immediately before the HD is stopped, if this time point does not coincide with a time point that is already scheduled.
- n. Dialysate samples for determination of MK-7264 will be obtained pre-dialysis, post-dialysis (immediately before the HD is stopped), and for 1 minute every half hour during HD.
- o. The HD session will be initiated immediately following the 2-hour postdose blood draw and the HD period will be approximately 4 hours in duration.
- p. To be performed on Day 4 of Period 2 or prior to early termination from the study.
- q. The clinic will contact all subjects (including subjects who terminate early) approximately 14 days after the last study drug administration to determine if any adverse events have occurred since the last study visit.

Abbreviations: C-I = Check-in, CRU = Clinical research unit, DNA = deoxyribonucleic acid, FBR = Future Biomedical Research, FSH = Follicle-stimulating hormone, FU = Follow-Up, HD = Hemodialysis, HIV = Human immunodeficiency virus, IRB/IEC = Institutional review board/independent ethics committee, P = Predose, PK = Pharmacokinetic.

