On Day 1 of Period 1, subjects with ESRD requiring HD will receive a single oral dose of MK-7264 immediately following their scheduled HD, followed by pharmacokinetic sampling for 72 hours. Subjects will initiate the next HD immediately following the 72-hour blood draw on Day 4. If the next scheduled HD must be initiated before 72 hours postdose, a sample for MK-7264 analysis will be collected prior to HD. Urine samples will be collected for 48 hours postdose, if possible.

On Day 1 of Period 2, subjects with ESRD requiring HD will receive a single oral dose of MK-7264 approximately 2 hours prior to their scheduled HD followed by pharmacokinetic sampling for 72 hours. The HD session will initiate immediately following the 2-hour blood draw. During this dialysis session, pre- and post-dialyzer plasma samples will be collected every 30 minutes during HD and dialysate samples will be collected pre-dialysis, post-dialysis, and for 1 minute every 30 minutes during HD for MK-7264 analysis. Urine samples will be collected for 48 hours postdose, if possible.

There will be a washout period of approximately 7 days (with 3 dialysis sessions) between MK-7264 dosing in Periods 1 and 2.

Both Parts:

Safety will be monitored throughout the study by repeated clinical and laboratory evaluations.

Subjects may be replaced at the discretion of the Sponsor.

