9.4 Treatments

9.4.1 Treatments Administered

Part 1:

Subjects will receive a single oral dose of 50 mg MK-7264 (1 x 50 mg tablet) at Hour 0 on Day 1.

Part 2:

Period 1: Subjects will receive a single oral dose of 50 mg MK-7264 (1 x 50 mg tablet) at Hour 0 on Day 1 immediately following their scheduled HD.

Period 2: Subjects will receive a single oral dose of 50 mg MK-7264 (1 x 50 mg tablet) at Hour 0 on Day 1, approximately 2 hours prior to their scheduled HD.

Both Parts:

MK-7264 will be administered following an overnight fast, with approximately 240 mL of water.

Subjects will be instructed not to crush, split, or chew the study drug.

The pharmacy at the CRU will provide each dose in individual unit dose containers for each subject.

The exact clock time of dosing will be recorded.

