11 DATA ANALYSIS

11.1 Pharmacokinetic Parameters

11.1.1 Plasma

For all subjects, pharmacokinetic parameters for plasma MK-7264 will be calculated as follows:

AUC0-last:	Area under the concentration versus time curve, from 0 to the time of the last quantifiable (above LLOQ) sample.
AUC0-∞:	Area under the concentration versus time curve from 0 to infinity after dosing.
AUC0-12:	Area under the concentration versus time curve, from 0 to 12 hours after dosing.
AUC0-24:	Area under the concentration versus time curve, from 0 to 24 hours after dosing.
AUC0-48:	Area under the concentration versus time curve, from 0 to 48 hours after dosing.
CL/F:	Apparent clearance after extravascular administration.
C _{max} :	Maximum observed plasma concentration after the administration of a given dose.
T _{max} :	Time to maximum observed plasma drug concentration.
t _{1/2} :	(Apparent) terminal half-life.
V _d /F:	Apparent volume of distribution during the terminal phase

No value for AUC0-∞, CL/F, V_d/F, or apparent terminal t_{1/2}, will be reported for cases that do not exhibit a terminal log-linear phase in the concentration versus time profile.

No pharmacokinetic parameters will be calculated for subjects with 2 or fewer consecutive time points with detectable concentrations.

Individual and mean plasma concentration time curves (both linear and log-linear) will be included in the final report.

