original scale. A two sided 90% CI for the true difference in means (ESRD HD - ESRD Non-HD) was calculated for each PK parameter (AUC0-last, AUC0- ∞ , Cmax, and CL/F) using the mean square error from the model and referencing a t-distribution. These confidence limits were exponentiated to obtain the 90% CI for the GMR (ESRD HD / ESRD Non-HD) for each PK parameter.

Other Pharmacokinetic Analyses

Subjects with moderate and severe RI and healthy matched control subjects (based on their BSA normalized eGFR) were re-categorized into different renal categories based on their BSA non-normalized eGFR and CrCL. Non-model based summary statistics by population were provided for AUC0-last, AUC0- ∞ , Cmax, CL/F and CLr.

Non-model-based %CV of the GM were presented for plasma MK-7264 AUC0-12, AUC0-24, AUC0-48, apparent terminal $t_{1/2}$, and Vz/F for subjects with moderate and severe RI, ESRD Non-HD, ESRD HD, and healthy matched control subjects. Individual values were also listed for each PK parameter by population and non-model-based descriptive statistics were provided.

Arithmetic mean (AM) concentration-time plots (with and without standard deviation [SD] error bars) of plasma, pre- and post-dialyzer plasma, and dialysate MK-7264 were presented by population on a linear-linear scale plot with an inset semi-log scale plot. The BLQ values were treated as 0 for the calculation of the AM (and SD, as appropriate). At the beginning of the profile, if < 50% of subjects had a quantifiable concentration \geq LLOQ for a given time point, the AM concentration was presented as 0. At the end of the profile when concentrations from some subjects began to fall BLQ, the AM value was only plotted if \geq 50% of subjects had quantifiable concentrations \geq LLOQ and the AM value was \geq LLOQ. However, all AM values were presented in the concentration tables. A reference line for the LLOQ value was added to the plot, where possible, as well as a footnote indicating the AM concentrations at or after certain time points that were not presented since > 50% of subjects had values < LLOQ or the AM was < LLOQ.

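### Vz/F from the hemodialysis period is not a volume of distribution: it rises as the reciprocal of the AUC0-∞ ratio even if distribution is unchanged

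*Protocol*

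**What the plan says.** Protocol 8.2 (Part 2) opens its list of further plasma parameters with "The following pharmacokinetic parameters will also be calculated for MK-7264 in plasma following the HD and non-HD dosing, as appropriate"; Vz/F is in that list. Protocol 11.1.1 describes the volume term only as "Apparent volume of distribution during the terminal phase" and gives no formula. Its one safeguard is that no value for AUC0-∞, CL/F, the volume term or terminal half-life "will be reported for cases that do not exhibit a terminal log-linear phase in the concentration versus time profile".

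On the timing of dialysis in Period 2, Protocol 6.2 (footnote o) says "The HD session will be initiated immediately following the 2-hour postdose blood draw" and "the HD period will be approximately 4 hours in duration". Protocol 9.1 has the dose given "approximately 2 hours prior to their scheduled HD followed by pharmacokinetic sampling for 72 hours".

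SAP 9.8.3 (Other Pharmacokinetic Analyses) says that summaries of Vz/F and several other parameters, not based on a model, were presented "for subjects with moderate and severe RI, ESRD Non-HD, ESRD HD, and healthy matched control subjects". Individual values and descriptive statistics were given by population as well. The modelled HD versus non-HD comparison (Protocol 11.2.3.3, SAP 9.8.3) covers AUC0-∞, AUC0-last, Cmax and CL/F. Vz/F is not in it.

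**The concern.** Vz/F describes a volume only if the clearance that produced AUC0-∞ is also the clearance acting in the terminal phase. That is true in Part 1 and in Period 1 of Part 2. In Period 2 it is not: from about hour 2 to hour 6 the subject has endogenous plus dialysis clearance, and afterwards endogenous clearance alone. AUC0-∞ carries the dialysis effect and λz does not, so their product no longer recovers the volume.

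The safeguard in Protocol 11.1.1 does not catch this. A clean log-linear decline after dialysis passes it, and the value is reported.

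What is at stake is interpretation. The ESRD HD summary of Vz/F stands beside four groups for which the parameter is valid. The documents carry no warning that it means something else there.

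**Working it through.** The documents give no Vz/F figure, so there is nothing to reproduce. The check is algebra followed by a simulation.

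**Inputs from the documents**
- Dose: 50 mg in both periods (Protocol 9.4.1).
- Dialysis: hours 2 to 6 of Period 2 (Protocol 6.2, footnote o).
- Sampling to 72 h (Protocol 9.1), which leaves 72 − 6 = 66 h after dialysis for λz.

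**Assumed**
- Vz/F = Dose/(λz × AUC0-∞).
- Dialysis clearance: not given; 3, 6 and 12 L/h were tried.
- Half-life in ESRD: Protocol 7.2.2 gives accumulation R of 1.4 to 1.5 with twice-daily dosing. From R = 1/(1 − e^(−12k)), k = −ln(1 − 1/R)/12, so the half-life is 6.6 to 7.6 h with normal renal function. Protocol 7.2.1 gives about 60% of a dose excreted. If that share of clearance is lost and volume is unchanged, the half-life becomes 6.6/0.4 to 7.6/0.4, about 17 to 19 h.

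**Step 1: algebra.** With equal dose and bioavailability F,

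Vz/F(HD) ÷ Vz/F(non-HD) = [AUC0-∞(non-HD)/AUC0-∞(HD)] × [λz(non-HD)/λz(HD)].

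If λz is the same in both periods, the second factor is 1 and the ratio is the reciprocal of the AUC0-∞ ratio. For an AUC0-∞ fall of d, the rise is 1/(1 − d) − 1:

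| Fall in AUC0-∞ | Ratio | Rise in Vz/F |
|---|---|---|
| 5% | 1/0.95 | 5.3% |
| 10% | 1/0.90 | 11.1% |
| 20% | 1/0.80 | 25.0% |
| 30% | 1/0.70 | 42.9% |

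In percent, the rise exceeds the fall. In a linear system with constant endogenous clearance, d is also the fraction of the absorbed dose that dialysis removes.

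**Step 2: does non-compartmental analysis at the planned times behave this way?** Oral models were simulated with true volumes held constant (absorption rate 2/h; half-life 17 h; one compartment of 100 L, or two compartments of 100 and 60 L with inter-compartmental clearance 20 L/h). Dialysis acted only at hours 2 to 6. AUC was computed by linear-up/log-down on the Part 2 sampling times, and λz by best adjusted R² on at least three points.

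| Model | Dialysis clearance (L/h) | AUC0-∞ ratio HD/non-HD | Vz/F ratio | 1/AUC0-∞ ratio |
|---|---|---|---|---|
| One compartment | 3 | 0.902 | 1.106 | 1.109 |
| One compartment | 6 | 0.814 | 1.227 | 1.228 |
| One compartment | 12 | 0.667 | 1.498 | 1.499 |
| Two compartments | 3 | 0.934 | 1.068 | 1.070 |
| Two compartments | 6 | 0.875 | 1.145 | 1.143 |
| Two compartments | 12 | 0.772 | 1.303 | 1.295 |

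The Vz/F ratio matches the reciprocal within about 1%, although the true volume never changes.

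**Step 3: what if λz differs?** A hypothetical second dialysis at hour 50 (one compartment, half-life 17 h) raised the estimated λz by factors of 1.042, 1.078 and 1.154. The Vz/F ratios were then 1.078, 1.166 and 1.350, against reciprocals of 1.123, 1.256 and 1.558. The bias is smaller but still upward.

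**The case against.** The strongest reply is that nothing planned depends on this value. Exploratory Objective 1 (Protocol 8.1.3) compares Vz/F between renal groups and healthy controls, not between HD and non-HD. The categorical model takes ESRD from Period 1 and does not include Vz/F (Protocol 11.2.3.2, SAP 9.8.3). No Vz/F ratio or interval is planned for HD against non-HD. All of this stands, and it limits the point to a descriptive summary in six subjects.

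A second reply is that Protocol 8.2 qualifies the list as applying where appropriate. The same list holds dialysis clearances, which cannot exist without dialysis, so it is not a promise to compute everything in both periods. That is fair to the protocol, but SAP 9.8.3 shows that Vz/F was in fact summarised for ESRD HD.

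A third reply is that equal λz is not guaranteed. Subjects are dialysed three times a week (Protocol 9.2.1.3), and the rule for a dialysis due before 72 hours is written for Period 1 only. This also stands. However, the Part 2 dosing dates in SAP 9.7, 28 and 29 July 2017, fall on a Friday and a Saturday. That fits a long interval to the next session, so a second dialysis within 72 hours looks unlikely.

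A reader might also infer that the HD versus non-HD contrast in CL/F is faulty. The documents do not support that. At a fixed dose CL/F is the reciprocal of AUC0-∞ in every group, not only under dialysis. No hypotheses are tested (SAP 9.8.3.3), so the contrast is not counted as separate evidence. The dialysis clearances proper are already planned (Protocol 7.2.3, 11.1.3, 11.2.3.3).

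**Conclusion.** The point holds and is minor. HD-period Vz/F is biased upward with no change in distribution. If λz and F are equal in the two periods, the factor is the reciprocal of the AUC0-∞ ratio: about 5%, 11%, 25% and 43% for AUC0-∞ falls of 5%, 10%, 20% and 30%. This rests on the standard formula and, for the exact factor, on no second dialysis altering λz within 72 hours.

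The actual size cannot be stated, because the documents give neither a dialysis clearance nor an AUC0-∞ ratio. The simulated figures show the mechanism and do not predict this drug's result.

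A reader might infer that the study set out to show, or would conclude, that dialysis changes distribution. The documents plan no such reading: Vz/F is exploratory and descriptive, and no primary estimate or interval uses it. What remains is that a number labelled as a volume is not one, and is displayed beside others that are.

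**What to change.** In Protocol 8.2 (Part 2), Protocol 11.1.1 and SAP 9.8.3, report Vz/F for ESRD from Period 1 (non-HD) only, and state the formula in 11.1.1. If the Period 2 value is kept, add a footnote wherever it appears: it is not a volume of distribution and is raised by the dialysis-induced fall in AUC0-∞.

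The cost is one descriptive column, or one footnote. No data are lost, because AUC0-∞, terminal half-life, the dialysis clearances and the amount recovered in dialysate are still reported for Period 2. The CL/F analysis needs no change.

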9 INVESTIGATIONAL PLAN

9.1 Overall Study Design and Plan

This is an open-label, 2-part, single dose study. In Part 1, the pharmacokinetics of MK-7264 will be evaluated in subjects with moderate and severe RI compared to healthy matched control subjects. In Part 2, the pharmacokinetics of MK-7264 will be evaluated in subjects with ESRD requiring HD under dialysis and non-dialysis conditions. Parts 1 and 2 of the study may be conducted concurrently.

Twenty-four (24), adult, male and female subjects between 18 and 80 years of age (inclusive) will be enrolled; 6 subjects with ESRD requiring HD, 6 subjects with severe RI, 6 subjects with moderate RI, and 6 healthy matched control subjects.

Once subjects with ESRD and subjects with severe and moderate RI are enrolled, the healthy matched control subjects will be enrolled. Each healthy control subject will be matched to the mean age (± 10 years) and weight (± 10 kg, where the weight is rounded to the nearest kg) of subjects with RI.

Screening of subjects will occur within 28 days prior to the first dose.

Assignment to a renal function group will be as follows:

Group	N	eGFR (mL/min/1.73m ²)*
Part 1		
Severe Insufficiency	6	<30 **, not on dialysis
Moderate Insufficiency	6	30 – 59 ***
Healthy Matched Control	6	≥ 90 ****
Part 2		
ESRD requiring HD	6	requiring HD

* eGFR based on MDRD equation at screening. Baseline eGFR will be obtained twice during the screening period, and the mean of the two values will be used for group assignment. The second baseline eGFR sample may be obtained at the time of check-in.

** Reasonable efforts will be made to enroll at least 2 subjects with eGFR values of < 20 mL/min/1.73m²

*** Reasonable efforts will be made to enroll at least 2 subjects with eGFR values of 30 - 45 mL/min/1.73m²

**** Healthy control subjects are within ± 10 years of the mean age and within ± 10 kg (where the weight is rounded to the nearest kg) of the mean weight for the pooled severe RI, moderate RI, and ESRD groups. For healthy subjects a creatinine clearance computed over a 24 hour urine collection for subjects that do not qualify with ≥ 90 eGFR may be done for confirmation purposes.

Part 1

On Day 1, a single oral dose of MK-7264 will be administered followed by pharmacokinetic sampling for 72 hours. Urine samples will be collected for 48 hours postdose, if possible.

Part 2:

Subjects with ESRD requiring HD will receive a single dose of MK-7264 on two occasions.

On Day 1 of Period 1, subjects with ESRD requiring HD will receive a single oral dose of MK-7264 immediately following their scheduled HD, followed by pharmacokinetic sampling for 72 hours. Subjects will initiate the next HD immediately following the 72-hour blood draw on Day 4. If the next scheduled HD must be initiated before 72 hours postdose, a sample for MK-7264 analysis will be collected prior to HD. Urine samples will be collected for 48 hours postdose, if possible.

On Day 1 of Period 2, subjects with ESRD requiring HD will receive a single oral dose of MK-7264 approximately 2 hours prior to their scheduled HD followed by pharmacokinetic sampling for 72 hours. The HD session will initiate immediately following the 2-hour blood draw. During this dialysis session, pre- and post-dialyzer plasma samples will be collected every 30 minutes during HD and dialysate samples will be collected pre-dialysis, post-dialysis, and for 1 minute every 30 minutes during HD for MK-7264 analysis. Urine samples will be collected for 48 hours postdose, if possible.

There will be a washout period of approximately 7 days (with 3 dialysis sessions) between MK-7264 dosing in Periods 1 and 2.

Both Parts:

Safety will be monitored throughout the study by repeated clinical and laboratory evaluations.

Subjects may be replaced at the discretion of the Sponsor.

